15 ETHICS AND REGULATORY REQUIREMENTS

15.1 Ethics review

It is the responsibility of the investigator to obtain written approval of the study protocol (incl. the patient information and informed consent) and subsequent protocol amendments from the IEC. The investigator should file all correspondence with the IEC, and a list of the IEC composition (names and position) should be filed in the Investigator File. A copy of the IEC approval should be forwarded to the sponsor.

15.2 Ethical conduct of the study

The study will be performed in accordance with the recommendations guiding physicians in biomedical research involving human patients adopted by the 18th World Medical Assembly, Helsinki, Finland, 1964 and later revisions and applicable ICH GCP guidelines.

The investigator is responsible for complying with all reporting procedures applicable to their IEC such as the reporting of SAEs and the final study report.

15.3 Written informed consent

It is the responsibility of the investigator to give each patient, prior to inclusion in the study, full and adequate verbal and written information regarding the purpose and procedures of the study and the possible risks involved. The patients must be informed about their right to withdraw from the study at any time, and that such withdrawal will not affect their future medical care, treatment or benefits to which the patient is otherwise entitled. The patients should be informed that the results will be stored and analysed digitally, maintaining confidentiality in accordance with local data protection laws.

Furthermore, it is the responsibility of the investigator to obtain signed informed consent from all patients prior to initiation of any study-related activity. As the study involves children, age specific patient information sheets and parent information sheets should be prepared, and patient and/or parental consenting should depend on the age of the patient. The investigator or his/her designated representative, who gave the verbal and written information about the study to the patient, must also sign the informed consent form. A copy of the written patient information must be handed to each patient, to bring home. The investigator will confirm the receipt of informed consent from each patient by a recording in the CRF. The signed Informed Consent forms should be filed by the Investigator in the Investigator File for possible future audits and inspections.

The investigator must always use the current IEC approved Patient Information/Informed Consent Form and it must not be changed without prior discussion with the sponsor and approval from the IEC.

15.4 Regulatory requirements

The study will be performed in compliance with each country's regulatory requirements. As with the IEC, clinical trial authorisation from the appropriate Regulatory Authority(ies) must be sought and obtained (as applicable to local country regulations), prior to the start of the study. The investigational product for this study will not be shipped to a study site until a copy of the applicable Regulatory Authority approval has been received by the sponsor. In addition, the Regulatory Authority(ies) must approve amendments (as instructed by OxThera), receive SUSAR reports and annual safety updates or as required by local country regulations, and be notified of the end of the trial.

16 DATA HANDLING AND RECORDKEEPING

16.1 Case report forms

A Case Report Form (CRF) is required and should be completed for each included patient. The CRF must be signed and dated by the investigator who takes responsibility for the accuracy, completeness and legibility of the data reported to the sponsor in the CRFs.

Data validation will be performed after data have been entered, signed and monitored by computerised logical checks. Any discrepancies found in the data will generate queries. The queries will be sent to the site personnel and the responsible site monitor for further action.

16.2 Retention of records

All essential documents must be safely retained by the investigator for at least 2 years following the date a marketing application is approved for the drug, for the indication for which it is being investigated; or if no application is filed or if the application is not approved for such indication for 15 years after the investigation is discontinued and the regulatory authorities are notified.

16.3 Protection of personal data

The completion of the Study involves the collection and processing of Personal Data. All processing of Personal Data at the clinic and by the sponsor must be carried out in accordance with national legislation concerning the protection of Personal Data.

The investigator must ensure that the patient's privacy is maintained. On the CRF or other documents submitted to OxThera, patients will be identified by a patient ID number only. Documents that are not submitted to OxThera (e.g., signed informed consent form) should be kept in a strictly confidential file by the investigator.

The investigator shall permit direct access to patient's records and source document for the purposes of monitoring, auditing, or inspection by OxThera, authorised representatives of OxThera, Regulatory Authorities and IECs.

As part of the required content of the informed consent, patients will be informed that their records may be reviewed by OxThera's designee and by regulatory agencies. Should access to medical record require a separate waiver or authorisation, it is the Investigator's responsibility to obtain such permission from the patient in writing before the patient is entered into the study.

17 FINANCING, INDEMNIFICATION AND INSURANCE

The Clinical Trial Agreement (CTA) outlines the compensation and payment terms of the study. The CTA must be signed before the start of the study. If there are differences between the CTA and the Protocol regarding certain rights and obligations the CTA is the prevailing document. Indemnification is covered by the CTA and by a separate Indemnification Agreement between the sponsor and the Institution if applicable.

OxThera has civil liability insurance, which covers this study in all participating countries.

18 CONFIDENTIALITY, INTELLECTUAL PROPERTY AND PUBLICATION POLICY

Investigator's, Institution's and OxThera IP AB's obligations regarding intellectual property, confidentiality and publication are described in detail in the CTA. They can be summarised as follows;

All information (whatever form) disclosed by OxThera to Institution, or generated pursuant to this study, shall be deemed to be confidential information. Except as required by applicable law, Institution shall not use or disclose to any party OxThera's confidential information received pursuant to this study or otherwise, without the prior written consent of OxThera. All data generated or arising from the performance of the study shall be the exclusive property of OxThera.

It is intended to publish the results of the study as a whole once all patients have completed the study and the study has been analysed. If there is a publication, the Investigator that has the highest number of treated patients will be the lead author. The investigator may not publish the results of their cohort of patients until the full study has been submitted for publication. The investigator may not submit for publication or present the results of this study without allowing OxThera 30 days in which to review and comment on the pre-publication manuscript. The investigator may not submit the results of the study for publication without the prior consent of OxThera, unless the review period has passed and there has been no reaction from the sponsor.

19 CHANGES TO THE STUDY PROTOCOL

The investigator should not implement any deviation from or changes to the protocol without agreement with the sponsor and prior review and documented approval from the IEC and Regulatory Authorities, except where necessary to eliminate an immediate hazard to the patients. All changes to the final study protocol must be documented in a written protocol amendment.

1 GENERAL

This Statistical Analysis Plan (SAP) describes in detail the methods and presentation of the data analyses which will be conducted by AUTHOR! et al. B.V. for study OC5-OL-01. This plan is written in agreement with protocol version 12, dated 14 October 2019, blank CRF version, dated 16 October 2019, and the relevant GCP-ICH guidelines. Furthermore, sponsor requirements for reporting are considered. Additional changes or updates of those documents or requirements may result in a new version of the reporting/statistical analysis plan.

A signed version of the SAP is to be finalized before first interim analysis.

2 STUDY INFORMATION

2.1 Study Objective(s)

The primary objective of this study is to evaluate the efficacy of OC5 to reduce total plasma oxalate levels during OC5 treatment in patients with Primary Hyperoxaluria (PH) who are on dialysis.

The secondary objectives of this study are:

- To evaluate the efficacy of OC5 to reduce free plasma oxalate levels during OC5 treatment in patients with Primary Hyperoxaluria (PH) who are on dialysis.
- To evaluate the safety of OC5 in patients with PH who are on dialysis.
- To evaluate changes in number of *O. formigenes* in faeces following administration of OC5.
- To evaluate effect of stopping OC5 treatment for 4 weeks after the first 6 weeks of treatment.
- To evaluate results from Speckle Tracking Echocardiography and traditional echocardiography.

2.2 Design of the Study

This study is an open label multi-centre study to evaluate the efficacy and safety of OC5 (Oxabact®) to reduce plasma oxalate in PH patients on dialysis.

The study is set up in two different treatment phases: the initial 14-week treatment phase (TRT) and the continued treatment phase (CT) for 36 months after week 14. Not all patients included in the TRT phase will continue into the CT phase.

2.3 Study medication

Patients will receive OC5 twice daily during the treatment phase and, if applicable, during the continued treatment phase.

2.4 Sample size

Approximately 6 to 12 patients will be enrolled in the study, to have a minimum of 6 patients completing the first year of continued treatment (i.e. week 52). It is estimated that 2 of the enrolled patients will be children.

The sample size is not based on assumptions of efficacy outcome and statistical power. Any inferences from the data will be based on clinical relevance rather than statistical significance.

2.5 Study flow chart

Table 1 Schedule of assessments – the first 14 weeks of the study

Study period:	Screening	Baseline				Treatment						Post-treatment			
Week:	-4 – 0 "0"	1	2	3	4	5	6	7	8	9	10	11	12	13	14
Clinic visit	1		2		3		4		5		6		7		8
Incl/Excl criteria¹	X				X										
Demographics	X														
Vital signs	X														X
Physical exam	X				X						X				X
PH Med History	X														
Medical history	X														
Concomitant med	X	X	X	X	X	X	X	X	X	X	X	X	X	X	
Pregnancy test	X														
Plasma oxalate		X	X	X	X	X	X	X	X	X	X	X	X	X	
Faeces			X							X					X
Safety Labs²	X			X						X					X
Treatment					X	X	X	X	X	X					
Adverse events						X		X		X		X		X	
Speckle Tracking Echocardiography	X ³														

1. Eligibility criteria will be evaluated at Screening and after Baseline. A stable dialysis regimen should be maintained for 2 weeks before start of baseline (2 weeks before visit week 2) and during the whole study.

2. Safety labs include: haematology analysis, clinical chemistry analysis and urinalysis and will be analysed at the local lab. Safety labs will be analysed at screening visit and at week 4, 10 and 14 +/- 1 week.

3. Speckle Tracking Echocardiography and traditional echocardiography should be done at screening visit +/- 1 month.

Table 2 Schedule of assessments – continued treatment Year 1 and 2

Study period	Continued treatment Year 1 and 2								
Week	0	4	8	12	16	20	24	28	32 ¹
Clinic visit	9 ²	10 ³	11	12	13	14	15	16	17
Vital signs			X		X		X		X
Physical exam			X		X		X		X
Concomitant med	X	X	X	X	X	X	X	X	X
Plasma oxalate	X	X	X	X	X	X	X	X	X
Faeces			X		X		X		X
Safety Labs⁴	X	X	X	X	X	X	X	X	X
Pregnancy test⁵	X						X		
Treatment	X	X	X	X	X	X	X	X	X
Adverse events	X	X	X	X	X	X	X	X	X
Speckle Tracking Echocardiography	(X) ⁶						X ⁷		

¹. Treatment will continue until the patient is transplanted. The maximal length of the continued treatment period will be 36 months. Visit intervals and examinations/samplings will be kept the same throughout the year 1 and 2 of the continued treatment period.

² Visit 9 may coincide with visit 8 for patients continuing on treatment immediately after week 14 visit.

³. Visit 10 will be scheduled 28 days (+/- 3 days) after first day of continued treatment after study week 14.

⁴. Safety labs include: haematology analysis, clinical chemistry analysis and urinalysis and will be analysed at the local lab.

⁵. Pregnancy test will be repeated every 6 months during the continued treatment period.

⁶. For patients who did not have a Speckle Tracking/Traditional Echocardiography performed at screening, an effort will be made to perform this examination before start of continued treatment.

⁷. Speckle Tracking/Traditional Echocardiography will be repeated every 6th month during the continued treatment period in weeks 0, 24, 48, 72 and 104.

Table 3 Schedule of assessments – continued treatment Year 3

Study period	Continued treatment Year 3			
Week	116	128	140	156
Clinic visit	28	29	30	31
Vital signs	X	X	X	X
Physical exam	X	X	X	X
Concomitant med	X	X	X	X
Plasma oxalate	X	X	X	X
Faeces	X	X	X	X
Safety Labs¹	X	X	X	X
Pregnancy test		X		X
Treatment	X	X	X	X
Adverse events	X	X	X	X
Speckle Tracking Echocardiography		X		X

1. Safety labs include: haematology analysis, clinical chemistry analysis and urinalysis and will be analysed at the local lab.

3 PATIENTS FOR ANALYSIS

3.1 Analysis populations

3.1.1 Full-Analysis-Set (FAS)

The FAS includes all patients who have received at least one dose of the investigational drug. This population will be used as primary analysis population for the analysis of efficacy.

3.1.2 Modified Full-Analysis-Set (mFAS)

The mFAS includes all patients who have received at least one dose of the investigational drug and have received at least one dose of the continued treatment phase. This population is used as additional analysis population for several post-hoc efficacy analyses during the CT phase.

3.1.3 Safety population

The safety population includes all patients who have received at least one dose of the investigational drug. The safety population is the same as the FAS for this study, and thus the FAS set wording will be used in all safety presentations.

4 BLIND DATA REVIEW MEETING

Protocol deviations will be identified to the extent possible by individuals responsible for data collection/compliance, and its analysis and interpretation.

Prior to database lock, the protocol deviations will be discussed during the (Blind) Data Review Meeting (BDRM). Invitees to this meeting are the OxThera Chief Medical Officer (CMO), the OxThera Statistician, the OxThera Project Manager (PM), the PSR Lead Data Manager (DM) and the AUTHOR! (Lead) Statistician, but more roles can be invited if considered necessary. Input to this meeting will be supplied by PSR PM/Data Management at least one week in advance of the meeting along with all protocol deviations identified during the study to the extent possible by individuals responsible for data collection/compliance, and its analysis and interpretation. The meeting is intended to resolve any outstanding data cleaning issues and consider the impact of certain protocol deviations on statistical analyses. Protocol deviations will be classified as important or not important.

The decisions taken during the meeting will be documented by the PM (or a delegate as agreed) and sent for review to all parties involved as soon as possible after the meeting, but before database lock. If all parties involved agree, then the document is finalized, signed by all attendees, and stored before database lock by the PM.

5 STUDY ENDPOINTS

5.1 Primary endpoint

The primary endpoint is change from baseline over time in total plasma oxalate level during OC5 treatment.

5.2 Secondary endpoint(s)

The secondary endpoints are the following:

- Change from baseline in free plasma oxalate level during OC5 treatment.
- Change in total plasma oxalate levels from week 10 to week 14, following the 4 week off-treatment period.
- Change from baseline in number of *O. formigenes* in faeces during OC5 treatment.
- Change from baseline in echocardiography parameters during OC5 treatment as measured by Speckle Tracking Echocardiography and traditional echocardiography.

5.3 Safety endpoint(s)

The safety parameters to be evaluated are:

- Adverse events.
- Laboratory safety measurements: haematology, clinical chemistry and urinalysis.

6 STATISTICAL ANALYSIS

6.1 General considerations

All evaluations will be explorative in nature, unless stated otherwise. There will be no formal statistical significance testing.

Raw data (in listings) will be presented in the same precision as received. Appropriate rounding will be performed for the summary statistics: arithmetic mean, median, SD (standard deviation) and two-sided 95% confidence limits will be presented with one more decimal than the original data; minimum and maximum values will be presented with the same precision as the original data. In special cases, e.g. after conversion of data, the number of decimals will be determined based on relevance. In frequency tables, percentages will be presented with 1 decimal unless otherwise stated. P-values will be presented with 3 decimals, and those smaller than 0.001 will be replaced by <0.001.

Descriptive statistics presented in summary tables for continuous variables will be the number of non-missing observations (n), arithmetic mean, SD, SE, median, Q1 and Q3, minimum and maximum. All plots will be created using scheduled protocol time or visit on the x-axis. Mean plots will be presenting mean +/- SE. For qualitative data, frequency counts and percentages will be determined. The denominator used when calculating percentages will be the number of subjects in the applicable analysis population.

Baseline is generally defined as the last non-missing and valid measurement/assessment before first dose of study drug. Unscheduled measurements are excluded as baseline value, unless otherwise specified. Change from baseline is calculated as the value at a specific time point minus the value at baseline. For this study, the following definitions are used to define the baseline measurement:

Vital signs: The screening value is used as baseline.

Plasma oxalate: The primary baseline is defined as an average of the available baseline measurements at weeks 2 and 4 (i.e. Visits 2 and 3 respectively). If one baseline measurement is missing for plasma oxalate, the remaining value will be used as baseline value. An additional baseline is the week 10 (Visit 6) assessment of plasma oxalate levels which will serve (only) as a baseline for the assessment of the change in plasma oxalate levels following the 4 week off-treatment period (secondary endpoint). For analyses in the CT phase of the study, a third baseline is defined, being the week 14 value at week 14 of the initial TRT phase.

Faeces: The measurement at week 4 is considered the baseline value.

Echography: The screening value is used as baseline. If this value is missing, the CT week 0 value is used as baseline value instead.

Safety lab: Safety lab is determined at screening and at week 4. The week 4 measurement is considered the baseline value. If this value is missing, the screening value will be used instead.

Data for screening failures will not be presented in summary tables, except for disposition and end-of-study displays, provided end-of-study data includes screen failures. Data for screening failures will be listed as available.

For this study, a treatment emergent adverse event (TEAE) is defined as an adverse event reported on or after first dose of study treatment. AEs after last dose date, and thus also after study drop-out, are not collected.

All descriptive statistics tables will be presenting data per visit, if applicable.

Any statistical significance determined in the analyses will be viewed with caution, considering the very small and heterogeneous patient population. Any determined p-values can only be indicative. No correction for multiple comparisons will be applied for any of the endpoints.

All collected data will be presented as is in individual data listings, and no other (calculated) data will be added unless specifically specified in the respective section. In case derived variables are to be added to the listings, both the original variable as well as the derived will be presented. For all relevant listings, study day will be added. The calculation for this day is as described in section 9.1.

6.2 Missing data

No imputation will be performed on missing data, except for those listed below. All analysis will be performed on data available at the visit considered. In summary tables, the number of patients without missing data will be presented (per visit, if applicable), unless otherwise specified. When dates are imputed, a flag will be provided to the CDISC datasets to show this is an imputed rather than an actual date. Listings will only present the actual date, but any calculations can be done on imputed dates.

AE and prior/concomitant medication

Missing/incomplete information related to AEs and concomitant medications will be handled as listed below, when applicable. Following these steps using temporary programming will ensure that missing dates imputations uses the most conservative approach.

- In case of a missing stop date, the stop date will be imputed as follows:
 - In case stop date is partially missing:
 - If the day part is missing, and the month and year present then day will be set to the last day of the month.
 - If both day part and month part are missing, then day and month will be set to 31 December of that year.
 - In case the stop date is completely missing and ongoing is not marked:
 - The event will be assumed to be 'ongoing'.
- In case of a partially missing onset/start date, and stop date is determined to be after first dose date (possibly after imputation), the start date will be imputed as follows:
 - In case start date is partially missing:
 - If the day part is missing, and the month is equal to the month of first dosing date, then day will be set to the date of first dose.
 - If the day part is missing, and the month is not equal to the month of first dosing date, then day will be set to the first day of the available month.
 - If both day part and month part are missing, then day and month will be set to January 1st of the year, unless if year is the same as first dose date year: then the date will be imputed with the first dose date.
 - In case the start date is completely missing:
 - If the stop date is earlier than the first dose date, then the start date will be set to Jan 1st of the stop year. If the stop date is on or after first dose date, then the start date will be set to first dose date.
- In stop date is before first dose date, then start date does not need an imputation, and the event or medication is considered to be prior.
- In case full start date and full stop date are missing, the start date will be imputed to first dose date.
- Missing severity will be imputed as severe.
- In case causality is missing for a certain TEAE, this will be regarded as related.
- In case seriousness is missing for a certain TEAE, this will be discussed and addressed prior to database lock and unblinding in agreement with CMO, PM and DM.

Medical History

For PH medical history, time since PH diagnosis and time on dialysis are calculated. If the date of diagnosis or earliest date of dialysis is partially missing, then the following will be applied:

- If only day is missing, the first day of the month will be used.
- If day and month are both missing, 1 January of the same year will be used.
- If full date is missing, no imputation will be done.

For MH in the year prior to enrollment, the following imputation method will be used for treated patients if medical history terms have a partially missing date, based on the principle that the most conservative approach would be to appoint the MH to the year before enrolment.

- If full start date is missing, the date will be imputed as 1 year prior to first dose date, and thus the MH will be included as part of the 1 year prior to enrolment.
- If start day and start month are both missing, and the difference between the year of first treatment and the start year of MH is larger than 1 year, then day and month are imputed with the first month and the first day of that month of the available year.

- If the difference between the year of first treatment and the start year of MH is 1 year, then the following applies:
 - If start day and start month are both missing, then:
 - If end month is available, then start months will be imputed with that month, and start day will be set to the first day of that month.
 - If no end month is available, then the month of reference date (i.e. the first dose date) is used combined with day+1 of that month.
 - If only start day is missing and start month is available, then:
 - If start month is the same as the month of the reference date (i.e. the first dose date), then start day is set to day+1 of that month.
 - If start month is not the same as the month of the reference date (i.e. the first dose date), then start day is set to the first day of the start month.
- If the difference between the year of first treatment and the start year of MH is 0, then the following applies:
 - If start day is missing, it will be set to the first day of the start month.
 - If both start day and month are missing, then day and month are imputed with the first month and the first day of that month of the available year.
- If end date is completely missing and ongoing is not applicable, then end year is study treatment year-1, end month is the same as the month of the reference date (i.e. the first dose date), and end day is day+1 of that month.
- If the end year is available and the difference between the year of first treatment and the end year of MH is larger than 1 year, then the following applies:
 - If both end month and end day are missing, then the end date will be imputed as 31 December of the available year.
 - If only end day is missing, then the end date will be imputed as the last day of the available month.
- If the end year is available and the difference between the year of first treatment and the end year of MH is 1 year, then the following applies:
 - If month and day are both missing, then month is set to the month of the reference date (i.e. the first dose date), and end day is set to the day of the reference date+1.
 - If only day is missing and month is the same as the month of the reference date, (i.e. the first dose date), then end day is set to day+1 of that month.
 - If only day is missing and month is different from the month of the reference date, (i.e. the first dose date), then end day is set to the last day of the available month.
- If the difference between the year of first treatment and the end year of MH is 0, then the following applies:
 - If both end day and month are missing, then month is imputed with the month of the reference date (i.e. first dosing date) and the end day is set to day-1 of that month, unless the day of the reference is the first day of the month, in which case end day will be set to the same day.
 - If only end day is missing, then the day will be set to the last day of the available month.

For untreated patients, it is not possible to determine MH in the year prior, as there is no reference date (i.e. first dosing date) available.

Plasma Oxalate during 4 -week treatment-off period

In case of missing values for week 10, 12 or 14, the method of LOCF will be applied to calculate CFB values.

Other

Other missing data occur for example during the CT phase, considering not all patients of the FAS will continue treatment. There will be no imputation for these missing values in the FAS population, and this may impact the results of the primary and secondary statistical analyses. Statistical results should therefore be viewed with caution.

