8.2 Concomitant medications

Any medications including over-the-counter medications or herbal supplements will be recorded as concomitant drug therapy on the case report form. Patients will continue any medications they are receiving at study entry for underlying medical conditions and the medications will be recorded at screening and changes will be noted throughout the study.

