6.7.4 Prior and concomitant medication

The use of prior and concomitant medication will be listed for all patients: included will be the medication generic name, WHO coding information, dose, route of administration, start and stop date, frequency and reason for administration, as well as information if given for an AE. A differentiation (flag) will be made between prior and concomitant medication.

In addition, summaries for prior and concomitant medications will be created, presenting the number of patients with any prior/concomitant medication, and the number of patients for each ATC System Main Therapeutic Group (2nd level of WHO classification), irrespective of duration of receipt, frequency or dose.

If a comedication is started prior to first dose of study treatment, this is considered prior medication. Concomitant medication is defined as started before first study treatment and continuing thereafter or starting on/after first dose date of study medication. As a consequence, several medications may be defined both as prior as well as concomitant. Whether a medication is considered prior/concomitant/both in case of partially missing dates is determined using the rules for missing data detailed in Section 6.2.

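### The date-imputation rule that SAP 6.2 shares between adverse events and medications classes some medicines in use before OC5 as concomitant only, when their start date is missing or known only to the first-dose year or month

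*SAP*

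**What the plan says.** SAP 6.2 sets out one procedure for both kinds of record: "Missing/incomplete information related to AEs and concomitant medications will be handled as listed below, when applicable". It states that the steps aim to be as conservative as possible. Four of its branches put the start on the day of first dose:

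- Start completely missing: "If the stop date is on or after first dose date, then the start date will be set to first dose date".
- Start and stop both missing: "In case full start date and full stop date are missing, the start date will be imputed to first dose date".
- Only the year known: 1 January of that year, "unless if year is the same as first dose date year: then the date will be imputed with the first dose date".
- Month and year known: "If the day part is missing, and the month is equal to the month of first dosing date, then day will be set to the" first-dose date. In any other month, the first of the month is used.

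SAP 6.7.4 then classifies medicines by date. For prior use: "If a comedication is started prior to first dose of study treatment, this is considered prior medication". For concomitant use: "Concomitant medication is defined as started before first study treatment and continuing thereafter or starting on/after first dose date of study medication". A medicine may be both. Where dates are partly missing, 6.7.4 refers back to the 6.2 rules.

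On collection, Protocol 8.2 says of medicines in use at entry that "the medications will be recorded at screening and changes will be noted throughout the study". Protocol 6.2.2 adds that changes are recorded at weeks 2 and 4. Treatment begins in week 5 (Protocol Table 4).

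**The concern.** For an adverse event, placing an unknown onset on the day of first dose makes the event treatment-emergent, which is the cautious direction. For a medicine the same step discards information that the study holds. A record made at screening or during baseline shows use before OC5, yet the rule ignores the visit of recording and derives a start on the first day of OC5. The medicine then fails the test for prior use.

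The same section does adapt its direction to the data type elsewhere: a medical-history item with no start date is placed one year before first dose. Medications get no such treatment.

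At stake is the description of treatment at entry. Protocol 12.1 reads this open-label, uncontrolled study as a set of individual case studies, so each patient's background medication should be described correctly. Two outputs are exposed: the prior-medication summary (14.1.6, a number that SAP 10.3 also gives to a medical-history table) and the prior/concomitant flag in the medication listing.

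**Working it through.** The plan states no figure to reproduce. The check applies the 6.2 imputation rules and then the 6.7.4 definitions to test records.

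**Inputs.** The rules are those quoted from SAP 6.2 and 6.7.4. The first-dose date is set to 16 June 2015, an arbitrary choice for illustration. A medicine marked as ongoing is taken to continue after first dose.

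**Tests.** Prior = imputed start before first dose. Concomitant = imputed start on or after first dose, or start before first dose with use continuing.

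| Start as recorded | Stop as recorded | Imputed start | Prior | Concomitant |
|---|---|---|---|---|
| 4 March 2010 | ongoing | 4 March 2010 | yes | yes |
| 2010 only | ongoing | 1 January 2010 | yes | yes |
| February 2015, no day | ongoing | 1 February 2015 | yes | yes |
| missing | 1 May 2015 | 1 January 2015 | yes | no |
| missing | ongoing | 16 June 2015 | **no** | yes |
| missing | 10 January 2016 | 16 June 2015 | **no** | yes |
| 2015 only | ongoing | 16 June 2015 | **no** | yes |
| June 2015, no day | ongoing | 16 June 2015 | **no** | yes |

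The last four rows lose the prior flag whatever the visit at which the medicine was recorded. By the 6.7.4 definitions, a medicine that is concomitant but not prior can only be one that began on or after first dose. The derived class therefore states something that a screening record contradicts. The first four rows are classified correctly.

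**Size of the date error.** Screening falls in weeks −4 to 0 and the first dose follows the week 4 visit, so a screening record precedes first dose by 4 − 0 = 4 to 4 − (−4) = 8 weeks. A medicine recorded then, with its start missing or known only to the year, has its derived start placed at least that much too late. The first-dose-month branch differs. There the true start lies in the same calendar month as the first dose, so the error is at most 31 − 1 = 30 days. That branch mainly concerns changes noted at week 2 or week 4.

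**Size of the effect on the table.** Protocol 11.5.1.2 gives 12 treated patients. SAP 6.7.4 counts patients with any prior medication and patients per ATC second-level group, not single medicines. One affected patient lowers a group's count by at most one: 1/12 = 8.3 percentage points. If the patient has another prior medicine in the same group, the change is zero.

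**The case against.** The strongest case on the other side is that this is a narrow housekeeping matter. Most of that case stands.

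- A long-standing medicine with any earlier year on record, or an earlier month of the dosing year, stays prior. A reader might infer that long-standing medicines in general drop out of the prior table; the rule does not do that.
- A reader might infer that medicines will appear to start together with OC5 and so cloud the efficacy reading. The documents do not support this. SAP 6.2 has listings print the actual date, which would be blank or partial, and flags imputed dates in the datasets. The medication summaries carry no dates, and no analysis in SAP 6.6 uses medication dates. Such medicines also remain in the concomitant-medication table (14.3.7).
- Vitamin B6 is a tempting example, because Protocol 8.2.1 bars its initiation during the study and the derived class would resemble an initiation. But inclusion criterion 6 requires a stable dose for at least 3 months before screening, so the site must establish its history. A B6 record with no start information is an unlikely case. The eligibility review and the protocol-deviation listing, not an imputed date, govern that question.
- The visit of recording is not among the listing fields in SAP 6.7.4, so a remedy that relied on it alone might not be programmable.

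None of this restores the correct class for the affected records. The listing still prints the prior/concomitant flag next to the blank date, and the prior-medication table carries no imputation flag.

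**Conclusion.** The point holds in a limited form and is minor. As written, SAP 6.2 and 6.7.4 together give a wrong class to a medicine known to have been in use before OC5, if it is still in use at first dose and its start is completely missing or known only to the first-dose year or month. No other passage corrects this. For medicines it works against the section's own aim of conservative handling.

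The consequence is confined to the prior-medication table and the listing flag. The size is at most 8.3 percentage points per affected patient in any one ATC group, assuming the 12 treated patients in Protocol 11.5.1.2 are the denominator. The documents do not give the number of records with such start dates. It may be zero.

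**What to change.** Keep the rule for adverse events. For medications, add to SAP 6.2:

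- A medicine is prior if its record was made at or before the week 4 visit (where the data show this), or if its missing or partial start date does not rule out a start before first dose.
- It is also concomitant if it continues on or after first dose.
- Its start is not imputed as the first dose date.

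The second condition in the first bullet works without the visit of recording, so the remedy does not depend on that field being in the database.

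Two wording repairs belong with this. Extend the cross-reference in SAP 6.7.4, which mentions only partly missing dates, to completely missing ones. Also move the rule for a completely missing start out from under the heading for partly missing starts in 6.2.

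The cost is one or two sentences and a small programming change. The downside is the reverse error: a few medicines truly begun on treatment, with no start date or one known only to the first-dose year or month, may also be counted as prior. The concomitant counts do not change for the records concerned.
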